12.5.1 Reporting a Pause

If a pausing criterion is met, a description of the AE(s) or safety issue must be reported by the principal investigator within 1 business day to the IRB by fax or email.

12.5.2 Resumption of a Paused Participant

The principal investigator will determine whether or not it is safe to resume administration of the study agent to the participant. The principal investigator will notify the IRB of the decision on resumption of the study agent.

12.5.2.1 Discontinuation of Study Agent for an Individual Participant

A participant who does not resume study agent will continue to be followed for safety.

12.6 Halting Rules for the Protocol

Halting the study requires immediate discontinuation of study agent administered for all participants and suspension of enrollment until a decision is made whether or not to continue enrollment and study agent administration.

The halting rules are:

- 2 or more participants experience the same or similar SAEs that are unexpected and possibly, probably, or definitely related to the study agent;
OR
- 2 or more of the same or similar AE in different participants that are grade 3 or above and are unexpected and possibly, probably, or definitely related to the study agent;
OR
- any safety issue that the principal investigator determines should halt the study.

The principal investigator will determine if the study should be halted.

12.6.1 Reporting a Study Halt

If a halting rule is met, a description of the AE(s) or safety issue must be reported by the principal investigator within 1 business day to the IRB by fax or email.

12.6.2 Resumption of a Halted Study

The principal investigator will determine if it is safe to resume the study. The principal investigator will notify the IRB of the decision on resumption of the study.

12.6.2.1 Discontinuation of Study Agent

Participants who do not resume study agent will continue to be followed for safety.

12.7 Study Discontinuation

The IRB, the NIAID, GSK, and other oversight bodies as applicable, as part of their duties to ensure that research participants are protected, may discontinue the study at any time. Subsequent review of serious, unexpected, and related AEs by the IRB may also result in suspension of enrollment and further trial interventions/administration of study agent.

12.8 Withdrawal Criteria for an Individual Subject

A study subject will be withdrawn for any of the following:

- An individual subject's decision. (The investigator should attempt to determine the reason for the subject's decision.)
- Non-compliance with study procedures (e.g., changing corticosteroid doses without principal investigator discretion, inability to comply with study visits) to the extent that it is potentially harmful to the subject or to the integrity of the study data.
- Any clinical AE, laboratory abnormality, intercurrent illness, other medical condition or situation that occurs such that continued participation in the study would not be in the best interest of the subject.
- The investigator determines that continued participation in the study would not be in the best interest of the participant.
- A change in the subject's baseline condition after enrollment so that the subject no longer meets the following eligibility criteria:
 - Development of pregnancy.
 - Development of a new malignancy (with the exception of localized skin cancer [basal or squamous] that may be cured by resection).
 - Withdrawal of permission for storage of study samples.
 - Permanent loss of decision-making capacity to provide informed consent.

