4.2 Recruitment Plan

EAE is an extremely rare disorder. A maximum of 12 intention-to-treat subjects with EAE will be enrolled with a ceiling of 15 patients for subjects that drop out prior to receiving the first dose. Subjects who are withdrawn prior to receiving mepolizumab will be replaced. The anticipated recruitment period will be 2 years. Subjects will be recruited from those already enrolled on NIH protocol 94-I-0079 (“Eosinophil activation and function in parasitic infections and other conditions with increased tissue or blood eosinophilia in humans”). The NIH is a major referral center for HES, with >200 patients actively followed on protocol 94-I-0079, of which 12 are known to have EAE, and 1-2 new patients referred for evaluation of eosinophilia weekly.

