4.3 Subject Inclusion Criteria

A subject will be eligible for participation in the study only if all of the following criteria apply:

- 1) The subject is male or female, aged 18 years or older.
- 2) The subject has a documented diagnosis of EAE.
- 3) The subject has symptoms of EAE in the cycle prior to screening, including but not limited to fever, swelling, hives or rashes, weight gain, muscle pain, and lymphadenopathy.
- 4) Cycling of eosinophils is ongoing as indicated by a peak AEC $\geq 1500/\text{mm}^3$ during at least one cycle in the prior 3 months.
- 5) If taking corticosteroids ≤ 40 mg daily, the subject is able and willing to stay on a stable dose for 6 weeks prior to screening.
- 6) The subject agrees to storage of study samples.

- 7) The subject is able to provide informed consent.
- 8) Females are eligible for this study if they are:
 - i. of non-childbearing potential (i.e., women who have had a hysterectomy or tubal ligation or are postmenopausal as defined by no menses in 1 year); OR
 - ii. of childbearing potential but willing to practice effective contraception or abstinence during administration of the study drug and for 100 days (5 terminal half-lives) after administration of the study drug.
 - iii. Not breastfeeding.

Participation of Women:

Pregnancy: The effects of mepolizumab on the developing human fetus are unknown. For this reason, women of childbearing potential must agree to use adequate contraception (see below for acceptable methods) prior to study entry, for the duration of study participation, and for >5 terminal half-lives (approximately 100 days) after administration of the last dose of study drug. Non-reproductive potential is defined as post-menopausal, male partner who has azoospermia or is surgically sterile (at least 6 weeks before screening) and is the sole sexual partner, surgical sterility, or a congenital or acquired condition that definitely prevents conception. Further, postmenopausal is defined as at least 12 consecutive months with no menses at age 50 or older, or a high follicle-stimulating hormone level in the postmenopausal range at ages 45-50 years in subjects not using hormonal contraception or hormone replacement therapy.

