6.6 Early Termination Visit

Subjects who desire to withdraw from study and further administration will be brought back for an early termination visit and clinical assessment. The principal investigator may also elect to terminate participation of the subject from the study for lack of adherence to study visits (according to the withdrawal criteria in section 12.8), safety (pausing or halting rules as described in sections 12.5 and 12.6), or lack of efficacy. Reasons for withdrawal and safety labs will be captured during this visit.

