 - Any loss or unanticipated destruction of samples (for example, due to freezer malfunction) or data (for example, misplacing a printout of data with identifiers) that meets the definition of a reportable event will be reported to the NIH IRB according to NIH Human Research Protections Program (HRPP) Policy 801.

- Additionally, subjects may decide at any point not to have their samples stored. In this case, the principal investigator will destroy all known remaining samples and report what was done to both the subject and to the IRB. This decision will not affect the subject's participation in other protocols at NIH.

10. Data Sharing Plan

Human data generated in this study will be shared for future research as follows:

- Identified data in the Biomedical Translational Research Information System (BTRIS)
- De-identified transcriptomic data in a public repository such as the National Center for Biotechnology Information Gene Expression Omnibus or Sequence Read Archive
- De-identified data with approved outside collaborators under appropriate agreements
- De-identified data will be shared with the public at the time of publication and/or public presentations

Data will be shared at the time of publication or shortly thereafter.

If this study and future research using samples and data collected in this study are expected to generate genetic data that triggers the NIH Genomic Data Sharing Policy, which applies to all NIH-funded research that generates large-scale human (e.g., transcriptomic data), the NIH Genomic Data Sharing Policy (<https://osp.od.nih.gov/scientific-sharing/policies/>) will be followed for deposition of data into the appropriate database (e.g., dbGaP).

11. Remuneration Plan for Subjects

Subjects will not be compensated for participation in this study, but will be reimbursed for out-of-pocket expenses related to at-home sample collection and their transportation costs as is permitted by the NIAID travel policy.

If in-person visits are performed remotely due to the COVID-19 pandemic, subjects will be reimbursed for the costs of remote procedures or the costs will be paid directly from study funds (e.g., shipping samples collected remotely).

12. Assessment of Safety

AEs and other reportable events are defined in NIH HRPP Policy 801: Reporting Research Events.

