12.8.1 Replacement of Withdrawn Participants or Participants Who Discontinue Study Agent

Participants who withdraw or are withdrawn from the study prior to receiving mepolizumab will be replaced. If a participant is replaced, all the data collected from that participant will still be included for the safety assessment.

13. Reporting Procedures

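### Section 12.8 withdraws a dosed subject who revokes sample storage, which ends endpoint collection that needs no stored sample

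*Combined protocol and SAP*

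**What the plan says.** Agreement to storage is inclusion criterion 6 in section 4.3: "The subject agrees to storage of study samples". Section 9 (Loss or Destruction) then lets a subject change that decision: "subjects may decide at any point not to have their samples stored. In this case, the principal investigator will destroy all known remaining samples". The same bullet protects the subject's place in other NIH protocols and says nothing about the place in this one.

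Section 12.8 supplies the consequence here. Its lead-in is mandatory, "A study subject will be withdrawn for any of the following", and one listed trigger, under changes that end eligibility, is "Withdrawal of permission for storage of study samples". There is no discretion for this trigger and no distinction between subjects before and after dosing.

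Replacement stops at the first dose. Section 12.8.1 states "Participants who withdraw or are withdrawn from the study prior to receiving mepolizumab will be replaced", and section 4.2 sets the enrolment maximum at 12 "with a ceiling of 15 patients for subjects that drop out prior to receiving the first dose".

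Section 6.6 provides an early termination visit with a clinical assessment, and adds "Reasons for withdrawal and safety labs will be captured during this visit". It describes no continued symptom log or series of blood counts after withdrawal.

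**The concern.** The two rules do different work. Section 9 gives effect to the subject's decision by destroying the samples. Section 12.8 goes further and ends participation, and with it the collection of data that have nothing to do with storage.

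The primary endpoint is built from the electronic daily log. Secondary endpoint 1 is the peak eosinophil count from serial CBCs, for which only the local laboratory's result is sent to NIH. Secondary endpoint 2 can be read from the Visit 8 CBC. Stored material serves the exploratory studies in Appendix H.

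Section 15.1 expects about five participants in a very rare disease, so losing follow-up on one dosed subject for a non-clinical reason could matter. It is also avoidable.

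**Working it through.** **1. Does either endpoint need a stored sample?** No.
- Symptoms: log entries (sections 6.1 and 7.1.3, Appendix E).
- Peak AEC: CBC with differential 2-3 times a week until Visit 6 (sections 6.1 and 6.3.3).
- AEC at Visit 8: CBC at that visit (section 6.3.6).

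**2. Does the plan elsewhere keep subjects whose research samples are not collected?** Yes. Section 6 lets the investigator waive research blood that cannot be shipped. Section 6.4.2 omits serum, urine and stored-cell collections at remote visits. Section 6.4.3 lists no research storage at Visits 11 to 13. Those subjects stay in the trial.

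**3. Secondary endpoint 1: reproduce the plan, then remove one subject.** Inputs from section 15.1: within-subject variance 0.01 on the log10 scale, so the paired difference has variance 2 × 0.01 = 0.02; true ratio 0.125; null ratio 0.25; one-sided 2.5%. The distance from the null is log10(0.25) − log10(0.125) = 0.301. Power is P(T > t), where T is noncentral t with n − 1 df and noncentrality 0.301 / √(0.02/n).

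| n | df | noncentrality | power |
|---|---|---|---|
| 5 | 4 | 0.301/0.0632 = 4.76 | 93.7% (plan: 94%) |
| 4 | 3 | 0.301/0.0707 = 4.26 | 80.0% |

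**4. Primary endpoint: reproduce, then truncate one subject.** Inputs from section 15.1: n=5, one baseline and three post-treatment cycles; Poisson mean a × e × f, with a gamma (mean 3, variance 3), e gamma (mean 1, variance 0.25), and f = 0.125 after treatment for an 87.5% reduction. The fit is quasi-Poisson with fixed person effects, dispersion not below 1, and t inference (14 df when complete). There were 40,000 simulated data sets per case.

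The plan's figures reproduce. Two-sided type I error is 4.8% (plan 4.9%) and one-sided 3.4% (plan 3.4%). Power is 91.2% (plan over 91%), and power to show at least a 30% reduction is 80.0% (plan 80%).

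| One of five subjects contributes | primary power | power to show ≥30% reduction |
|---|---|---|
| all 3 post-dose cycles | 91.2% | 80.0% |
| 2 post-dose cycles | 89.4% | 77.5% |
| 1 post-dose cycle | 86.9% | 73.3% |
| none | 81.3% | 65.8% |

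With fixed person effects, a subject with baseline data only adds nothing to the treatment estimate, so the last row matches n=4 (81.4%). These figures count data sets with no post-treatment symptoms at all as failures. Counting them as successes gives 92.2% complete and 83.7% in the last row, which is the same picture.

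**5. When can the loss occur?** On the model schedule in Appendix B, a subject who de-escalates is on study from first dose to end for 267 − 15 = 252 days. The first post-dose peak is captured by Visit 6 (Day 43), so secondary endpoint 1 is exposed for at most 43 − 15 = 28 days, or 28/252 = 11%. After Visit 8 (Day 99) only exploratory data remain, for 267 − 99 = 168 days, or two thirds.

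**6. At the stated sample size.** Going from 12 to 11 subjects, primary power moves from 99.97% to 99.89%, and secondary power is 100% to one decimal at both.

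**7. Frequency.** The documents give none. Purely as an assumption, take 1% to 5% of subjects revoking, all at the worst time. The chance of at least one in five is 1 − 0.99⁵ = 4.9% to 1 − 0.95⁵ = 22.6%. Multiplying by the 9.9-point fall (91.2 − 81.3) gives an expected primary loss of about 0.5 to 2.2 points, a little more at the upper end if two subjects revoke.

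**The case against.** The rule is coherent on its face. Storage is an entry criterion, the mechanistic aims rely on stored material, and section 12.8 treats revocation as a loss of eligibility. The trigger is probably rare, the large power figures need revocation before any post-treatment data at n=5, and the stated sample size is 12. All of that stands, and it limits the size of the point. It does not explain why a subject whose samples are waived for travel stays while one who revokes storage must leave.

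Four stronger readings are tempting and are not supported.
- A reader might infer that the subject's existing efficacy data are thrown away. The documents do not say so; they are silent on whether those data stay in the analysis.
- A reader might infer that the rule gains nothing. That is a judgement. What the text shows is that no stored sample is recovered. The rule does keep participation aligned with criterion 6, and the documents give no rationale either way.
- A reader might infer that early termination yields nothing but reasons and safety labs. Section 6.6 also provides a clinical assessment.
- A reader might infer that subjects are not told of this consequence. The consent pages were not available, so that cannot be judged.

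One further objection also stands. The primary endpoint is defined after three doses, so for a subject who revokes before Visit 7, continued logs and counts match that definition only if dosing is completed. That question has to be settled alongside the follow-up rule.

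**Conclusion.** The point holds as a minor, inexpensive improvement. As written, section 12.8 ends unreplaceable primary and secondary endpoint collection for a dosed subject over a decision that touches neither endpoint, and section 9 destroys the samples in any event.

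The fall of about 10 points for the primary endpoint and 14 for secondary endpoint 1 is a worst case. It rests on the plan's own models, on n=5, on one subject lost, and on revocation before any post-treatment data. The cost shrinks with each cycle completed and with more subjects. It is not evidence that the trial is underpowered.

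**What to change.** Keep agreement to storage as an entry criterion. For subjects who have received mepolizumab, replace the storage bullet in section 12.8 with a statement that:
- collections for storage stop and stored samples are destroyed under section 9;
- scheduled symptom logs, CBCs and safety assessments continue through the primary endpoint assessment if the subject agrees;
- data already collected stay in the efficacy analysis.

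The end of daily logging must be reconciled at the same time. Section 7.1.3 runs it through Visit 8, whereas section 6.1 and the notes to Table 1 in Appendix B stop it after Visit 7. Whether study drug continues after revocation is for the sponsor and investigator to state; no dosing rule is proposed here.

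The cost is a short text change in section 12.8 and, if the consent form carries the same rule, a matching change there. The subject's stored exploratory samples are lost under either rule.

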12.8.1 Replacement of Withdrawn Participants or Participants Who Discontinue Study Agent

Participants who withdraw or are withdrawn from the study prior to receiving mepolizumab will be replaced. If a participant is replaced, all the data collected from that participant will still be included for the safety assessment.

13. Reporting Procedures

13.1 Reporting to the NIH IRB

Reportable events will be tracked and submitted to the NIH IRB according to HRPP Policy 801.

13.2 Reporting to the NIAID Clinical Director

The principal investigator will report unanticipated problems (UPs), major protocol deviations, and deaths to the NIAID clinical director according to institutional timelines.

14. Clinical Monitoring Structure

To help ensure that NIH Office of Research Support and Compliance procedures and GCP are being carried out, a Clinical Trials Management designee within the Office of Clinical Research Policy and Regulatory Operations, Regulatory Compliance and Human Subjects Protection Program will conduct a study initiation visit before study enrollment begins. The purpose of this meeting is to review with the principal investigator and study team designees the roles and responsibilities concerning their commitment to adhere to the requirements of the protocol, especially in terms of NIH OHSRP reporting requirements for AEs, SAEs, and UPs. In addition, the quality management and data management plan for the study will be reviewed.

14.1 Quality Management Plan

During the study, the principal investigator and study team will be responsible for implementing a quality management plan. Additionally, the study team will be responsible for completing and submitting a summary report on the quality plan to the NIAID Clinical Director or designee at least annually as detailed in the quality management plan. A courtesy copy will also be sent to Clinical Trials Management.

14.2 Safety Monitoring Plan

The data gathered during this study will be monitored by the principal investigator for safety and compliance with protocol-specified requirements.

15. Statistical Considerations

15.1 Study Hypotheses, Endpoint and Sample Size Justification

This is a pilot study designed as proof of principle, and the small sample size is dictated both by our ability to recruit sufficient numbers of patients in this rare disease and the complexity of the study design.

First, based on the fact that there are n=12 subjects already in the natural history protocol, we expect to be able to get n=5 subjects to participate in this study.

For the primary endpoint of change in maximum daily AE score (DAES), we use a quasi-Poisson model to estimate the average percent reduction after treatment compared to pre-treatment. This model accounts for within-person correlation of

the repeated maximum DAES by allowing a different (fixed) person effect for each person, and it also allows overdispersion from the Poisson model. Because of the small sample sizes and to be conservative, we allow for overdispersion but not underdispersion and use a t-distribution for inferences. We calculate power to show that the percent reduction is greater than 0. We simulate the maximum DAES values using $n=5$ individuals measured for 4 cycles using a Poisson model with random effects for each individual (to induce within-person correlation) and additional extra-Poisson variation for each observation. Specifically, for the i^{th} individual at the j^{th} cycle, the DAES is distributed Poisson with mean: $a_i * e_{ij} * f_j$, where a_i is distributed gamma with mean 3 and variance 3 (this models the per-person average baseline maximum DAES such that 8% have values less than 1, 58% are less than 3, and 94% are less than 6), e_{ij} is distributed gamma with mean 1 and variance 0.25, and $f_j = 1$ when $j=1$ for the baseline cycle and $f_j = 1-(r/100)$ for the cycles after treatment, where r is the percent reduction. We first simulate 10,000 data sets under the null hypothesis of 0% reduction. The simulated the type I error rate for the two-sided test is 4.9% (close to the nominal 5%); however, the one-sided type I error rate is slightly inflated at 3.4% (for a nominal 2.5%). This slight inflation is due to the small sample size and because of this, we will make two-sided inferences. Next we simulate 10,000 data sets with 87.5% reduction and show that we have over 91% power to show a significant effect at the two-sided 5% level. For the analysis we will present two-sided 95% confidence intervals which can show larger effects than just the difference from 0. For example, the simulations show that with an 87.5% reduction we have 80% power to show that the percent reduction is at least 30% (i.e., 80% of the simulated 95% confidence intervals show percent reductions of at least 30%).

Now consider the power of the secondary endpoint. Review of cycles occurring in subjects collected to date for whom we had 2 consecutive peaks in the absence of medication changes shows a typical variation of 4-30% from cycle to cycle. One subject had a change of 37% from peak eosinophils from one cycle (AEC 12100/mm³) to the next (AEC 7600/mm³). A primary endpoint requiring reduction of eosinophils by 75% would be double the highest variation in any individual and would not be likely to occur without concurrent administration of medications such as glucocorticoids in these individuals based on our experience in managing these patients. As such, we can provide a rough estimate of the power of the study to show that the percent reduction in peak AEC in subjects after receiving mepolizumab is more than 75%.

We model the peak AEC using a linear model on the log transformed peak AEC values. Let Y_{ij} be the $\log_{10}(\text{peak AEC})$ for subject i at cycle j , where $j=1$ is baseline and $j=2$ is the first cycle after baseline (and the first peak after treatment). The model is $Y_{ij} = m_i + b(j-1) + e_{ij}$ where m_i is the random effect for the i^{th} subject distributed normally with mean u and variance v_m , i.e., $m_i \sim N(u, v_m)$ and the errors are $e_{ij} \sim N(0, v)$. We use preliminary data on 5 subjects with 2 peaks to estimate u , v_m , and v . We get $u=4.2$, $v_m=0.05$ and $v=0.01$. We assume

that the effect $b=\log 10(0.125)$, so that the model predicts a ratio of geometric means of post-treatment peak AEC over baseline peak AEC of 12.5%. This corresponds to an 87.5% reduction in peak AEC. We simulate from this model with 10,000 data sets with $n=5$ subjects in each data set. The simulated power to show at the one-sided 2.5% level that the percent reduction in peak AEC is more than 75% (i.e., the ratio of post-treatment to baseline is less than 25%) is 94%.

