We hypothesize that IL-5–driven eosinophilia is central to the pathogenesis of EAE. Suppression of eosinophil cycling by blocking IL-5 would help determine whether eosinophils are indeed the main drivers of the symptoms of angioedema and urticaria and pave the way for future mechanistic studies investigating the etiology of this unusual disorder. The purpose of this pilot study is to evaluate the effect of mepolizumab, a humanized antibody to IL-5, on eosinophil cycling in 12 subjects with EAE. Subjects with EAE will undergo screening on the National Institutes of Health protocol 94-I-0079 to establish the periodicity of their cycling (if not previously determined) and the optimal timing for the baseline visit. After screening, subjects will be followed closely with signs and symptoms recorded in a daily log and daily and monthly questionnaires, as well as complete blood counts and research blood collected for one cycle prior to administration of mepolizumab. Subjects will receive a total of 3 monthly administrations of mepolizumab at 700 mg, followed by drug de-escalation over 6 additional monthly administrations for subjects who demonstrate benefit from mepolizumab. All subjects will have a follow-up visit about 1 month after the last study administration of mepolizumab.

The primary efficacy endpoint will be reduction of symptoms and severity of symptoms after mepolizumab. Secondary endpoints will include reduction in peak eosinophils after mepolizumab, continued suppression of absolute eosinophil count and reduction in symptoms following monthly dosing of mepolizumab therapy.

1. Background Information and Scientific Rationale

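### The plan states 12 subjects, but every power and error figure is for 5; at 12 the power is higher and the two-sided type I error is about 6.5%, not 4.9%

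*Combined protocol and SAP*

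**What the plan says.** The size appears in four places.

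- The Protocol Summary lists a sample size of 12 and an accrual ceiling of 15.
- The Précis gives the purpose as evaluating the drug's effect "on eosinophil cycling in 12 subjects with EAE".
- Section 4.2 says "A maximum of 12 intention-to-treat subjects with EAE will be enrolled with a ceiling of 15 patients", the ceiling allowing for dropouts before the first dose. It adds "Subjects who are withdrawn prior to receiving mepolizumab will be replaced" and "The anticipated recruitment period will be 2 years".
- Section 15.1 notes that 12 subjects are in the natural history protocol and then says "we expect to be able to get n=5 subjects to participate in this study".

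All simulations in section 15.1 use n=5. For the primary endpoint (maximum daily symptom score per cycle) the data are generated "using $n=5$ individuals measured for 4 cycles". The reported figures are a two-sided type I error of 4.9%, a one-sided error of 3.4% against a nominal 2.5%, over 91% power for an 87.5% reduction, and 80% power to show a reduction of at least 30%. For peak absolute eosinophil count (AEC) the stated power is 94%. The one-sided inflation is put down to the small sample size and given as the reason for making two-sided inferences. No figure is given for n=12, and nothing connects the 5 to the 12.

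**The concern.** A reader who takes the trial size from the summary and the operating figures from section 15.1 is combining two different trials. For power this errs on the safe side if more than 5 subjects are treated. For type I error the n=5 figure cannot be assumed to carry over, and section 15.1 rests its choice of two-sided inference on that figure being close to 5%. If the error is higher at 12, the 95% confidence intervals the plan intends to report are less reliable at the stated size than the document says.

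**Working it through.** **Inputs (section 15.1).** The person effect "is distributed gamma with mean 3 and variance 3" (shape 3, scale 1). The per-observation effect "is distributed gamma with mean 1 and variance 0.25" (shape 4, scale 0.25). There is one baseline and three post-treatment cycles. Counts are Poisson with mean a·e·f, where f = 1 at baseline and 1 − r/100 afterwards. The analysis is quasi-Poisson with fixed person effects, dispersion not below 1, and a t reference.

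**Formulas.** Let B be the total baseline count and P the total post-treatment count.

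- Log rate ratio: b = log((P/3)/B)
- Variance: φ(1/B + 1/P), with φ = max(1, Pearson χ²/df)
- df = 4n − n − 1 = 3n − 1, so 14 at n=5 and 35 at n=12
- A reduction is shown if the upper 95% limit of b is below 0; a reduction of at least 30% if it is below log(0.7)

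**Peak AEC.** The log10 ratio has variance 2v = 0.02. The distance from the 75% threshold is log10(0.25) − log10(0.125) = log10(2) = 0.301.

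- n=5: noncentrality 0.301/√(0.02/5) = 4.76, critical t on 4 df = 2.776, power 93.7%
- n=12: 0.301/√(0.02/12) = 7.37, critical t on 11 df = 2.201, power above 99.9%

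**Results (100,000 simulated data sets per primary-endpoint scenario; ranges are across repeat runs).**

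| Figure | Plan, n=5 | Recomputed, n=5 | Recomputed, n=12 |
|---|---|---|---|
| Power, 87.5% reduction | over 91% | 91.1% | above 99.9% |
| Power to show at least 30% | 80% | 79.9% | 99.6% |
| Type I error, two-sided | 4.9% | 4.7–4.9% | 6.5–6.7% |
| Type I error, one-sided | 3.4% | 3.4–3.5% | 3.8–4.0% |
| Peak AEC power | 94% | 93.7% | above 99.9% |

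The n=5 column reproduces the plan. If subjects with no symptoms in any cycle are dropped from the degrees of freedom, n=5 power is 88.7%, while the two-sided error hardly moves (4.8% at n=5, 6.5% at n=12).

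**Why the error rises with n.** At n=5 the 4.9% is the sum of two unequal tails: 3.4% towards benefit and, by subtraction, 4.9 − 3.4 = 1.5% towards harm. The excess in one tail is offset by the deficit in the other. At n=12 the tails are 3.8% and 2.6%, both above 2.5%.

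The underlying cause looks like the variance model. Under the simulated data, a subject with mean a has variance a + 0.25a², so variance/mean = 1 + 0.25a: 1.25 at a=1 and 2.5 at a=6. Quasi-Poisson assumes one ratio for everyone. Averaging over subjects equally gives about 1 + 0.25×3 = 1.75. The totals B and P weight subjects by a, and E(a²) = 3 + 3² = 12, so the ratio needed is about 1 + 0.25×12/3 = 2.0. The standard error is then too small by a factor of about √(1.75/2.0) = 0.935, and a nominal 5% test behaves like one with cut-off 1.96 × 0.935 = 1.83, or roughly 6.7%. This is a rough large-sample argument, but it agrees with the simulation and does not depend on n being small.

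**The case against.** The best defence is that the two numbers fit together: 5 is a recruitment forecast for a very rare disease, 12 is a cap, and computing power at the pessimistic number is prudent. That stands for power. The flat 12 in the Protocol Summary and Précis is then loose wording. It does not stand for type I error, which is worse at the cap than at the forecast.

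It is also fair to say that the 6.5–6.7% comes mainly from the analysis model rather than from the mismatch of sizes, so harmonising the numbers would disclose the error, not remove it. That is correct. But reporting n=5 only is what keeps it out of sight, and it contradicts the stated explanation.

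Three stronger readings are tempting and are not supported:

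- **That no limit independent of results exists.** Section 4.2 sets one: 12 treated, a ceiling of 15, replacement only before dosing, and an anticipated 2-year recruitment period. What is missing is a sentence making these the closing rule and placing the primary analysis after it.
- **That enrolment could be stopped when open-label results look good, inflating the error further.** Section 15 describes no interim analysis and no early stop for efficacy. Error rates for repeated testing would describe a procedure that is not in this plan. Section 15.1 also gives 5 as an expectation, not a minimum.
- **That the target effect is unclear.** Section 15.1 states it: an 87.5% reduction for both endpoints, against 0% for symptoms and against 75% for peak AEC.

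**Conclusion.** The inconsistency is real, and more than editorial in one respect. Power is understated for a trial of 12, which does no harm. Two-sided type I error is understated by about 1.6 to 1.8 percentage points (6.5–6.7% against 4.9%) and one-sided by about 0.4 to 0.6 points (3.8–4.0% against 3.4%). The attribution of the one-sided inflation to small numbers is not borne out, since the inflation grows from n=5 to n=12.

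These results assume the protocol's own data model and four complete cycles per subject. If the real data have less variation between observations, or a different mean–variance relation, the error at 12 will differ. The n=5 calculation itself is correct. This is a modest correction to a pilot's statistical section, and it does not undermine the design.

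**What to change.** - State the size in the same terms in the Protocol Summary, Précis, section 4.2 and section 15.1, for example 5 expected and 12 maximum.
- In section 15.1, report power, two-sided type I error and the at-least-30% figure at both n=5 and n=12, with peak AEC power alongside.
- Replace the statement that two-sided error is close to nominal with the figure at each size, and remove or correct the attribution of the inflation to small sample size.
- Add one sentence: enrolment closes at 12 dosed subjects or at the end of the 2-year accrual period, whichever comes first, and the primary analysis is run once after that.

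The cost is a rerun of the existing simulation with one input changed and a few lines of text. No subjects, visits or procedures are added. The downside is a slightly less favourable stated type I error. Bringing that error back to 5% at n=12 would need a change to the variance model, which is a separate decision.
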